4. STATISTICAL METHODS

4.1. Sample Size Justification

No formal sample size calculations were performed. The proposed sample size will allow for initial estimates of efficacy as well as provide for sufficient safety information to be obtained, while still limiting the number of subjects exposed to the IP.

4.2. General Statistical Methods and Data Handling

4.2.1. **General Methods**

All output will be incorporated into Microsoft Excel or Word files, sorted, and labeled according to the International Council on Harmonisation (ICH) recommendations, and formatted to the appropriate page size(s).

Tabulations will be produced for appropriate demographic, baseline, efficacy, pharmacokinetic and safety parameters. For categorical variables, summary tabulations of the number of missing, and number and percentage of each category of the parameter will be presented by treatment groups and visits (as applicable). For continuous variables, the n, mean, standard deviation, median, minimum, and maximum values will be presented.

The baseline visit will be defined as the last non-missing measure prior to initiation of investigational treatment. Differences between treatment groups will be calculated as OTX-CSI minus HV, and change from baseline will be calculated as follow-up visit minus baseline visit values.

All statistical testing will be done at the two-sided alpha level of 0.05.

Sponsor:	Ocular Therape	Ocular Therapeutix, Inc.			
Protocol:	CLN-Protocol-0054				
Document Version No.:	V1.0	V1.0 Document Date: 01-OCT-2021			

4.2.2. Unit of Analysis

Both eyes will be treated with the same treatment/formulation. If both eyes qualify, the eye having the higher total corneal fluorescein staining score will be designated as the study eye and the other eye designated as the non-study eye. If both eyes have the same total corneal fluorescein staining score, the study eye will be designated randomly, and the other eye designated as the non-study eye. If only one eye qualifies, that eye will be the study eye, but both eyes will still receive the same treatment/formulation.

The unit of analysis in this study will be the study eye (primary study eye) for all efficacy summaries. Efficacy summaries will be presented for both study and non-study eyes for Cohort 1 and Cohort 2. Cohort 1 will be included for all safety summaries and will include summaries of both study and non-study eyes. All primary, sensitivity, secondary, and exploratory endpoints will be analyzed for both study and non-study eyes, separately. All summaries will be presented by treatment groups and visits, where appropriate. In addition to summarizing the individual formulations, the two formulations of OTX CSI will be combined and summarized.

4.2.3. **Computing Environment**

All descriptive statistical analyses will be performed using SAS statistical software (Version 9.4), unless otherwise noted. Medical History and adverse events will be coding using Medical Dictionary for Regulatory Activities (MedDRA) version 24.0 - Mar 2021. Concomitant medications will be coded using World Health Organization (WHO) DD B3 WHO Drug DDE – Sep 2019.

4.2.4. Methods of Pooling Data

The two OTX formulations will be combined and summarized as well as individual formulations.

4.2.5. **Adjustments for Covariates**

The statistical modeling of change from baseline for each variable will be adjusted for its baseline value.

4.2.6. Multiple Comparisons/Multiplicity

As this is a Phase 1/2 study, no adjustments to alpha will be made for testing of multiple endpoints.

Sponsor:	Ocular Therape	Ocular Therapeutix, Inc.			
Protocol:	CLN-Protocol-0054				
Document Version No.:	V1.0	V1.0 Document Date: 01-OCT-2021			

4.2.7. **Subpopulations**

No analyses of subgroups of subjects are planned.

4.2.8. Withdrawals, Dropouts, Loss to Follow-up, replacement

Any subject who wishes to voluntarily discontinue study drug or withdraw from participation in the study for any reason is entitled to do so without obligation.

IP may be discontinued (insert removed) and any subject may be discontinued from study participation at any time during the study at the discretion of the Investigator or the Sponsor for any reason.

In the event that study discontinuation of a randomized subject is necessary, the Investigator should make every attempt to have the subject complete Visit 8 assessments as soon as possible. The reason for premature discontinuation should be recorded in the subject chart and entered in the eCRF.

Subjects who withdraw from Cohort 1 will be replaced. Subjects who withdraw from Cohort 2 will not be replaced.

4.2.9. Missing, Unused, and Spurious Data

If the start date of an AE is partially or completely missing, the date will be compared as far as possible with the date of the start of administration of study drug. The AE will be assumed to be treatment-emergent if it cannot be definitively shown that the AE did not occur or worsen during the treatment-emergent period (worst case approach). The imputed dates will only be used to classify events as treatment emergent and will only be used in the table analyses. Listings will display the available date data.

The following general rules will be used:

- If the start day is missing but the start month and year are complete, an AE will only be excluded as being treatment-emergent if the start month/year is before the month/year of study drug administration or if the date of resolution is before study drug administration.
- If the start day and month are missing but the start year is complete, an AE will only be excluded as being treatment-emergent if start year is before the year of study drug administration or if the date of resolution is before study drug administration.
- If the start date is completely missing, an AE will be considered treatment-emergent unless the date of resolution is before study drug administration.

Sponsor:	Ocular Therape	Ocular Therapeutix, Inc.			
Protocol:	CLN-Protocol-0054				
Document Version No.:	V1.0	V1.0 Document Date: 01-OCT-2021			

4.2.9.1. Imputation Method for Efficacy Endpoints

To impute missing, Markov Chain Monte Carlo (MCMC) multiple imputation (MI), Fully Conditional Specification multiple imputation (FCS MI) and last observation carried forward (LOCF) methods will be used.

For MI, we will have below phases:

1. Imputation Phase: in this phase, the missing data will be imputed using SAS PROC MI and a complete data set will be created. This process of imputation will be repeated 25 times. Therefore, 25 compete datasets will be created. In this phase, treatment group, baseline value, and post-baseline visits from visit 3 to visit 8, respectively, will be included in multiple imputation model.

2. Analysis Phase: each of the 25 complete data sets will be analyzed independently using desired statistical method (e.g. ANCOVA for primary efficacy analysis).

3. Pooling Phase: in this phase the estimates obtained from each analyzed complete dataset from phase 2, will be combined using PROC MIANALYZE.

The analysis of efficacy variables Schirmer Test, Eye Dryness Severity Score and Eye Dryness Frequency Score on mITT and PP populations will be performed by imputing missing data using MCMC MI methodology with repeated 25 times of imputation under the assumption of missingness at random. Last observation carried forward (LOCF) method and Fully Conditional Specification multiple imputation (FCS MI) with 200 burn-in iterations and 25 times of imputation under the assumption of missingness at random will be used for sensitivity analyses (Section 4.7.2). LOCF method will be used for sensitivity analyses.

4.2.10. Visit Windows

Visit windows will be calculated based on the schedule of assessments in Table 1. Any visits or procedures performed outside the scheduled visits must be documented in the Unscheduled Visit page of the eCRF. Although there is a visit window around the expected visit date, nominal visits will be used for the per-visit analyses.

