7.6.2 Collection of Data from Withdrawn Subjects

In the event that study discontinuation of a randomized subject is necessary, the Investigator should make every attempt to have the subject complete Visit 8 assessments as soon as possible. The reason for premature discontinuation should be recorded in the subject chart and entered in the eCRF.

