Study Parameter*	Screening/ Baseline Visit Day -14	Insertion Day Day 1	Follow-up Week 2 ±2 days	Follow-up Week 4 ±2 days	Follow-up Week 6 ±3 days	Follow-up Week 9 ±3 days	Follow-up Week 12 ±3 days	Final Visit Week 16 ⁸ ±3 days	30-Day Follow-Up Visit ⁹ (± 10 days)
Visit	1	2	3	4	5	6	7	8	9
Randomization (Cohort 2)		Х							
OTX-CSI or HV Insert Placement		X ^{11 & 12}							
Ease of Insertion as assessed by the Investigator		Х							
Dispense Artificial Tears (as needed)	Х	Х	Х	Х	X	Х	Х		
Dispense Daily Subject Diary for Artificial Tear Use (as needed)	X	Х	Х	Х	X	х	Х		
Collect/review Daily Subject Diary for Artificial Tear Use (as needed)		Х	Х	Х	X	Х	Х	Х	

*All examinations need to be performed on both eyes. See Section 8.4 to confirm the order that the assessments should be performed.

1 A negative UPT is required for women of childbearing potential to be included in the study.

- 2 Select sites will collect Systemic PK. All sites will collect Tear Film PK.
- 3 Dilated fundus examination at screening; undilated fundus examination at Week 16.
- 4 Prior to insertion, a clinical determination of the absence of infection will be made based on the lack of erythema or discharge at the punctum.
- 5 Systemic PK sample on Day 1 will be collected after successful insertion at 2 hours (±30 minutes) or 4 hours (±30 minutes) post-insertion.
- 6 Tear Film PK will be collected at 1 hour (±30 minutes), 2 hours (±30 minutes), and 4 hours (±30 minutes) post insertion on Day1. Tear Film PK should be collected using Schirmer strips.
- 7 Tear Film PK will be collected using Schirmer Tests strips. These will be collected and sent to the central lab for analysis. See lab manual.
- 8 Early termination subjects should complete assessments based on the final visit (Visit 8) schedule of assessments.
- 9 Post week 16 visit will be conducted every 30 days (± 10 days) until an insert can no longer be visualized and the physician has determined that there is no evidence of biological activity. Additionally, subjects may be exited at the investigator's discretion
- 10 Signs, symptoms, conditions occurring prior to insertion on Day 1 should be captured as medical history.

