LogMAR Visual Acuity (VA) score for each visit, its CFB, and loss of 3 Lines or more in BCVA LogMAR Score from Baseline at each post-baseline visit will be calculated and summarized using descriptive statistics.

2- Slit-Lamp biomicroscopy

The evaluation of normal, mild, moderate, severe, and very severe for each eye in Eyelid Vascularity (vascular engorgement) and Vascular Engorgement of Eyelid Margin of upper and lower lid, as well as normal, abnormal non-clinically significant, and abnormal clinically significant for each eye in Punctal Appearance, Lid Apposition, Lashes, Conjunctiva, Sclera, Cornea, Anterior Chamber, Iris, Pupil, and Lens will be tabulated for each visit by using the frequency and percentage.

3- Intraocular Pressure (IOP) measurement (mmHg)

Absolute value at baseline and visit 8 (week 16), its CFB, absolute IOP measurement \geq 30 mmHg at each visit, and CFB in IOP > 5 mmHg as well as >10 mmHg at Visit 8 will be summarized using descriptive statistics.

4- Fundus Examination

The evaluation of normal, abnormal non-clinically significant, and abnormal clinically significant for each eye in vitreous, retina, macula, choroid, and optic nerve exam will be tabulated for visit 1 and visit 8 by using the frequency and percentage. The absolute cup-to-disc ratio at baseline and Visit 8 (Week 16) and its CFB at Visit 8 (Week 16) will be presented using descriptive statistics.

5- Artificial tears use during the study

The use of artificial tears, based on the Daily Subject Diary, since last visit will be tabulated for each post-baseline visit by using frequency and percentage. Number of times AT used since last visit will be reported among all subjects who have any daily subject dairy data since the last visit using descriptive statistics.

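### The 30-Day Follow-Up tests compare subjects retained mainly because an insert is still visible; separately, early-termination values have no stated analysis visit

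*SAP*

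**What the plan says.** **30-Day Follow-Up.** SAP 4.7.3 lists this visit with Visits 3 to 8 for lissamine green staining, OSDI and SPEED. All are to be analysed like the Schirmer test, on observed data, in the mITT and PP populations. The contrasts are the six in SAP 4.7.1: F1, F2A and the two combined, each against F2B and against F3. Under SAP 2.1 (and Protocol 6.1), a subject returns after Week 16 if an insert is seen in either eye. A subject with no visible insert and no evidence of biological activity exits, and the investigator may exit a subject at any time. SAP 1.1 gives designed persistence of about 2 to 3 months for F1, 3 to 4 months for F2A and F2B, and 1 week for F3.

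**Early termination.** For a subject who discontinues, Protocol 7.6.2 says "the Investigator should make every attempt to have the subject complete Visit 8 assessments as soon as possible", and SAP 4.2.8 repeats it. Footnote 8 of SAP Table 1, attached to the Week 16 column, adds: "Early termination subjects should complete assessments based on the final visit (Visit 8) schedule of assessments". SAP 4.2.10 says "Although there is a visit window around the expected visit date, nominal visits will be used for the per-visit analyses". The same section also says: "Any visits or procedures performed outside the scheduled visits must be documented in the Unscheduled Visit page of the eCRF". For multiple imputation, SAP 4.2.9.1 says "post-baseline visits from visit 3 to visit 8, respectively, will be included in multiple imputation model". In SAP 4.9, IOP is summarised as "Absolute value at baseline and visit 8 (week 16), its CFB", and the fundus findings "will be tabulated for visit 1 and visit 8 by using the frequency and percentage".

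**The concern.** Randomisation protects a comparison only if the groups compared are those that were randomised, or a subset whose selection does not depend on treatment. Attendance at the 30-Day Follow-Up depends on whether the insert has lasted, and how long it lasts is a designed property of the product assigned. If subjects who keep an insert longer also differ in their dry eye outcome, a difference between arms appears with no drug effect. The p-value would still carry an mITT label.

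The early-termination question is one of labelling. A subject who leaves at Week 3 has a Week 3 measurement taken under the Visit 8 schedule. With nominal visits and no rule for such values, a Visit 8 label turns it into a Week 16 result. That would touch the Week 16 efficacy analyses and the IOP and fundus tables, for which Visit 8 is the only scheduled post-baseline visit. It would also enter the MCMC imputation model.

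**Working it through.** The plan gives no sample size calculation, dropout rate, SD or effect size, so there is no figure of its own to reproduce. The arm sizes do follow from 2:2:2:1: 140 × (2, 2, 2, 1)/7 = 40, 40, 40, 20.

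**1. 30-Day Follow-Up: which contrasts are affected**

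Week 16 is 112 days; 112/30.44 = 3.7 months. That is past F1's designed life, within that of F2A and F2B, and far past F3's.

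| Contrast | Designed persistence |
|---|---|
| F1 v F2B | differs |
| F2A v F2B | same |
| F1 + F2A v F2B | differs (F1 part) |
| F1 v F3 | differs |
| F2A v F3 | differs |
| F1 + F2A v F3 | differs |

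Five of six differ. If 0% to 10% of F3 subjects keep an insert (assumed), 0 to 2 of 20 attend, so the three F3 contrasts are empty or nearly so.

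**2. 30-Day Follow-Up: size for F1 v F2B with no true effect**

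Assume that the fraction p of an arm with the longest persistence attends, and that persistence correlates r with outcome (bivariate normal). The mean shift among attenders is r·φ(z)/p SD, where z cuts off the top p. The false difference is r·[φ(z₁)/p₁ − φ(z₂)/p₂], and its standard error is √(1/n₁ + 1/n₂) SD.

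| p, F1 v F2B | n | r | φ(z)/p | False difference (SD) | SE (SD) | Error at nominal 5% |
|---|---|---|---|---|---|---|
| 0.25 v 0.40 | 10 v 16 | 0.2 | 1.271, 0.966 | 0.061 | 0.403 | 5.2% |
| 0.10 v 0.60 | 4 v 24 | 0.4 | 1.755, 0.644 | 0.444 | 0.540 | 12.5% |

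The error rates are from the noncentral t distribution. The direction follows the sign of r, which is unknown. For F2A v F2B the difference is zero if attendance is equal, and 0.06 to 0.13 SD at 40% v 60%.

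**3. Early termination: what the text settles**

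The withdrawal sections and footnote 8 fix which assessments are done. None of them says under which visit the record is filed. SAP 4.2.10 points to the Unscheduled page for visits outside the schedule. Both readings are open, and the eCRF is not available.

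**4. Early termination: size if labelled Visit 8**

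Assumed inputs: a 3 mm effect building to Week 12; SD 6 mm; every dropout gives a termination visit, uniform over Weeks 0.5 to 15.5; baseline plus six visits, with constant correlation 0.6 or correlation decaying to 0.5 over 12 weeks. The method is joint normal imputation followed by ANCOVA on baseline, with Monte Carlo SE at most 0.021 mm. The 0 to 35 bounds in the SAP's code were not modelled.

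- Share of Week 16 values taken before Week 14: d × (14 − 0.5)/15. For d = 5% this is 4.5% (about 2 of 40); for d = 20% it is 18% (about 7 of 40).
- Standard error for 40 v 40 with complete data: 6 × √(1 − 0.6²) × √(2/40) = 1.07 mm; with correlation 0.5, 1.16 mm.

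| Equal random dropout | Week 12, MCMC (mm) | Week 16 (mm) |
|---|---|---|
| 5%, constant correlation | −0.017 | −0.068 |
| 5%, decaying | −0.039 | −0.060 |
| 20%, constant correlation | −0.073 | −0.261 |
| 20%, decaying | −0.169 | −0.267 |

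The shifts fall by roughly half if only half of dropouts give a termination visit. At 20% dropout they are at most 0.016 mm (Week 12) and 0.023 mm (Week 16) if the full effect is present from Week 2.

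**5. Early termination: the other routes**

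- Values discarded (Unscheduled page): the largest MCMC shift is 0.017 mm at Week 12 and 0.020 mm at Week 16.
- Values assigned by study day to the nearest visit: 0.035 and 0.031 mm.
- FCS: the code in SAP 7.3.3 regresses Week 12 (AVAL8) on treatment, baseline and earlier visits only, so Week 12 is unaffected (−0.005 to +0.006 mm). Observed-data Week 12 results are unaffected too.
- MCMC: the code in SAP 7.3.2 lists AVAL9 (Visit 8 by its place in the sequence), which is how a mislabelled value reaches Week 12.

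**The case against.** On the 30-Day Follow-Up, SAP 4.7 already limits reporting to observed data. The tests cover three secondary instruments after the Week 12 endpoint, in a Phase 1/2 study without multiplicity control. The modelled bias is below one standard error and rests on assumed attendance and correlation; at the low end the error rate barely moves. All of this is true and bears on weight. But restricting the tests to observed data does not restore comparability, because the observed subjects are the selected ones.

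On early termination, a reader might infer that early values will be analysed as Week 16. The documents do not establish this: they say which assessments are done, not how the record is labelled, and the Unscheduled page is at least as well supported. A reader might also infer that the Week 12 primary result is materially biased. Only the MCMC imputations are touched, indirectly, and only under the Visit 8 label. Larger shifts can be produced: −0.57 mm at Week 16 and −0.35 mm at Week 12 with random dropout, and −0.84 and −0.55 mm with outcome-dependent dropout. All four need 40% dropout in the active arm against 20% on vehicle, which nothing in the documents suggests. Finally, no IOP or fundus value is lost, since Listings 16.1.19 and 16.1.20 cover both tests.

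**Conclusion.** The 30-Day Follow-Up point holds on the SAP's own text. Five of six contrasts compare subsets formed after randomisation by designed persistence, and the three F3 contrasts may be nearly empty. F2A v F2B share a designed persistence, so it would be wrong to say that all six are distorted in this way, though that contrast too uses a post-randomisation subset. The size, 0.06 to 0.44 SD for F1 v F2B, rests wholly on assumed attendance and correlation.

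The early-termination point is a real gap in specification with a conditional consequence. Under a Visit 8 label and equal dropout of 5% to 20%, the Week 16 effect is about 0.06 to 0.27 mm too low and the imputed Week 12 effect 0.02 to 0.17 mm too low. At most that is about a quarter of a standard error. On the Unscheduled reading there is no material bias. Priority is low for the primary result. It is somewhat higher for the Week 16 efficacy tables and for IOP and fundus, where an early leaver's value is either shown as Week 16 or appears only in listings.

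**What to change.** 1. **SAP 4.7.3:** make the 30-Day Follow-Up descriptive only. Give the number attending by arm, with no tests. Because the visit repeats every 30 days, also say which record is summarised. The cost is the loss of p-values that are not randomised comparisons.
2. **SAP 4.2.10:** state that early-termination values before Week 14 (the midpoint of Weeks 12 and 16) are not analysed as Visit 8, whichever eCRF page holds them. Either exclude them from the per-visit analyses, or assign them by study day to the nearest scheduled visit and keep the scheduled value where one exists. Exclusion is simpler and shows equal or lower bias. In simulation at 20% dropout its Week 12 standard error was 1% to 2% larger (1.166 v 1.155 mm; 1.269 v 1.248 mm). Assignment by study day is a preference, not a necessity.
3. **SAP 4.2.9.1:** apply the same rule to the MCMC, FCS, LOCF and observed-data analyses.
4. **SAP 4.9:** show early-termination IOP and fundus values in a separate row, not as Week 16.

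This takes a few sentences, one extra row in two sets of tables and a small change to the visit derivation, all before unmasking. It assumes that assessment dates are on the eCRF. No new data or visits are needed.

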8.3 Study Assessments by Visit

For every visit, perform study procedures as referenced in the Schedule of Events (Appendix 1) in the order specified below in both eyes. Note: Procedures will apply to both Cohort 1 and Cohort 2 unless otherwise indicated. An asterisk (*) indicates the assessment may occur at any time during the visit.

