8.3.9 Final Visit 8 (Week 16 ±3 days)

- Record concomitant medications *
- Record AEs *
- Collect and review Subject Daily Diary for Artificial Tear Use (as needed) *
- Urine pregnancy test (WOCBP only)
- VAS for Eye Dryness
- OSDI
- SPEED assessment
- BCVA assessment
- Slit lamp biomicroscopy, including punctum assessment
- OTX-CSI or HV Insert Presence by visual Assessment
- Ease of Visualization by Investigator
- Corneal fluorescein staining (NEI scale)
- Conjunctival Lissamine Green Staining (NEI scale)
- Schirmer Test (without anesthesia) and Tear Film PK

Note: Wait 20 minutes prior to conducting Schirmer/Tear Film PK

- Undilated Fundus Exam (*may be performed before or after IOP)
- IOP
- Punctum Size Assessment
- Dispense artificial tears (as needed)
- Dispense Daily Subject Diary for Artificial Tear Use (as needed)

Note: All ophthalmic assessments must be performed on both eyes.

8.3.10 30-day Follow-Up Visit (Week 20 ± 10 days)

This visit will be conducted every 30 days (\pm 10 days) until an insert can no longer be visualized and the physician has determined that there is no evidence of biological activity.

- Record concomitant medications *
- Record AEs *
- Collect and review Subject Daily Diary for Artificial Tear Use (as needed) *
- VAS for Eye Dryness
- OSDI
- SPEED assessment
- BCVA assessment
- Slit lamp biomicroscopy, including punctum assessment
- OTX-CSI or HV Insert Presence by visual Assessment
- Ease of Visualization by Investigator
- Corneal fluorescein staining (NEI scale)
- Conjunctival Lissamine Green Staining (NEI scale) Schirmer Test (without anesthesia) and Tear Film PK Note: Wait 20 minutes prior to conducting Schirmer/Tear Film PK
- Dispense artificial tears (as needed)
- Dispense Daily Subject Diary for Artificial Tear Use (as needed)

Note: All ophthalmic assessments must be performed on both eyes.

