8.3.12 Unscheduled Visit

An unscheduled visit may be performed during the course of the trial in order to ensure subject safety. All procedures performed at an unscheduled visit will be recorded in the source documents and on the Unscheduled Visit eCRF pages.

Evaluations that may be conducted at an Unscheduled Visit may include:

- Slit lamp biomicroscopy
- BCVA assessment
- IOP
- Dilated or Undilated fundus exam
- Urine pregnancy test (if applicable)
- Assessment of AEs
- Assessment of concomitant medications and/or treatments
- Any other assessments needed in the judgment of the investigator

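### SAP 4.9 counts safety threshold events by nominal visit, with no worst-post-insertion row and no rule for unscheduled readings; the gap is mainly for IOP and fundus

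*SAP*

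**What the plan says.** **Labelling of visits.** SAP 4.2.10 first directs off-schedule work to its own form: "Any visits or procedures performed outside the scheduled visits must be documented in the Unscheduled Visit page of the eCRF". It then says: "Although there is a visit window around the expected visit date, nominal visits will be used for the per-visit analyses".

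**Summaries.** SAP 4.9 covers IOP with "Absolute value at baseline and visit 8 (week 16), its CFB". It adds IOP of 30 mmHg or more at each visit, and IOP rises above 5 and above 10 mmHg at Visit 8. For vision it says "loss of 3 Lines or more in BCVA LogMAR Score from Baseline at each post-baseline visit will be calculated". Slit-lamp findings are tabulated for each visit, and fundus findings for Visits 1 and 8. The planned outputs (Tables 14.3.6 to 14.3.9) are all titled by visit.

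**Unscheduled visits.** Protocol 8.3.12 says: "An unscheduled visit may be performed during the course of the trial in order to ensure subject safety". Its list of possible evaluations includes slit lamp, BCVA, IOP and a fundus exam. All four are secondary safety evaluations in Protocol 6.2.1.

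**Other outputs.** The SAP plans by-subject listings of BCVA, slit lamp, IOP and fundus on the Safety population (Listings 16.1.17 to 16.1.20). Its TEAE tables are not tied to particular visits.

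**The concern.** Readings taken at an unscheduled visit are often taken because something seemed wrong, so they carry more safety information than a routine reading. If the threshold tables are filled from nominal visits alone, an arm can show no IOP rise above 10 mmHg although one was measured and entered on the eCRF. A reader comparing arms looks at the tables, not at the listings.

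IOP is the most exposed measure because the schedule has only one routine reading after insertion. The silence on unscheduled readings also leaves room for two programmers to produce different counts for the 30 mmHg and three-line rows from the same data.

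**Working it through.** The plan gives no event rate or sample-size figure to reproduce (SAP 4.1 states that no formal calculation was done). The check is a count of scheduled readings, a comparison with SAP 4.9, and simple arithmetic for scale.

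**1. Scheduled readings after insertion (Protocol 8.3 and Appendix 1).** IOP appears at Visits 1, 2 and 8. Protocol 8.3 instructs sites to "perform study procedures as referenced in the Schedule of Events (Appendix 1) in the order specified below in both eyes". At Visit 2, IOP is listed ahead of the eligibility decision and insert placement, so it is a pre-insertion value. Visits 3 to 7 and Visit 9 have no IOP. Subjects who leave early are asked for the Visit 8 assessments at exit.

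- IOP: 1 of the 6 visits from Visit 3 to Visit 8, or 1 of 7 with the first Visit 9.
- Fundus: Visit 8 only, so the same 1 of 6.
- BCVA and slit lamp: 6 of 6, and again at Visit 9.

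**2. Schedule against summary.**

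| Summary | Scheduled after insertion | Counted in SAP 4.9 | Place for an unscheduled reading |
|---|---|---|---|
| IOP rise >5, >10 mmHg | Visit 8 | Visit 8 | None |
| Fundus category | Visit 8 | Visits 1 and 8 | None |
| IOP ≥30 mmHg | Visit 8 | Each visit | Not stated |
| BCVA loss ≥3 lines | Visits 3 to 9 | Each post-baseline visit | Not stated |
| Slit-lamp category | Visits 3 to 9 | Each visit | Not stated |

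The 30 mmHg row is thinner than it looks. Exclusion 7 bars IOP above 24 mmHg, and Protocol 7.3 requires this still to hold at Day 1. For an eligible subject, the only scheduled reading that could reach 30 mmHg is therefore the one at Visit 8.

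**3. Size of one uncounted subject.** The share is 100 × 1/n, with planned arm sizes from SAP 2.1 and exact (Clopper-Pearson) 95% intervals.

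| n | Without the subject | With the subject |
|---|---|---|
| 40 | 0% (0 to 8.8%) | 2.5% (0.06 to 13.2%) |
| 20 (HV Formulation 3) | 0% (0 to 16.8%) | 5.0% (0.13 to 24.9%) |
| 80 (both OTX-CSI arms) | 0% (0 to 4.5%) | 1.25% (0.03 to 6.8%) |

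**4. How much a single Week 16 IOP reading can see.** This is an illustration under assumptions that are not in the documents: one IOP episode per affected subject, timed uniformly over 16 × 7 = 112 days, lasting d days. The chance that the Week 16 reading falls inside it is d/112: 7/112 = 6%, 14/112 = 13%, 28/112 = 25%.

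For a 40-subject arm with a true proportion p affected, the chance that at least one episode occurs is 1 − (1 − p)^40. The chance that at least one is seen at Week 16 is 1 − (1 − p·d/112)^40.

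| p | At least one occurs | Seen, d = 7 | Seen, d = 14 | Seen, d = 28 |
|---|---|---|---|---|
| 5% | 87% | 12% | 22% | 40% |
| 2% | 55% | 5% | 10% | 18% |

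These figures show why any unscheduled IOP reading matters. They do not measure what the analysis rule loses, because most of the difference comes from episodes that nobody measured.

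**The case against.** The strongest reply has four parts.

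**The visit-window sentence does not exclude anything.** It decides whether an early or late scheduled visit is labelled by its nominal number or by date. A reader might infer that unscheduled readings are barred from every safety table and that such events are never counted. The SAP does not say so. For the 30 mmHg, three-line and slit-lamp summaries it is silent. This part stands. It does not reach the IOP-rise and fundus rows, which name their visits.

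**Other outputs carry these events.** Adverse events are the primary safety evaluation. They are recorded from Visit 2 through Visit 9 whatever their severity or cause, and AE assessment is among the options at an unscheduled visit. The listings should show the reading itself. This stands in part: no IOP or BCVA threshold in the documents obliges an investigator to report an AE, a preferred-term table does not give the prespecified threshold rate, and a listing gives no rate by arm.

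**Sparse IOP sampling is a separate matter.** A reader might take one scheduled reading in about 112 days as the size of the analysis problem. It is not. It describes the schedule, and an any-time row leaves it unchanged. Likewise, a brief vision loss between the Week 12 and Week 16 visits is recovered only if an unscheduled visit happened to catch it. This stands.

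**BCVA and slit lamp are well covered.** Both are examined at every follow-up visit, so they should not be put on a par with IOP. This stands.

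**Conclusion.** The point holds as a reporting gap. The threshold summaries are per nominal visit, no worst-post-insertion row is planned, and unscheduled readings have no stated handling. For IOP rises above 5 and 10 mmHg and for fundus findings, a reading made only at an unscheduled visit has no cell in Tables 14.3.7 and 14.3.9. For IOP of 30 mmHg or more, three-line BCVA loss and slit-lamp findings, the treatment is undefined. BCVA and slit lamp carry the smaller risk because of their frequent scheduled examinations.

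Each affected subject is worth 2.5 points in a 40-subject arm, 5 points in the 20-subject arm and 1.25 points in the 80 pooled OTX-CSI subjects. How many there would be is unknown: the documents give no rate of unscheduled visits or of IOP rises. The conclusion rests on the plain wording of SAP 4.9 and the table titles, and on unscheduled readings keeping that label and not being assigned to a nominal visit. The documents do not support the claim that such events vanish from the report, since listings and reported AEs remain. This is a worthwhile, inexpensive improvement to the safety tables.

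**What to change.** In SAP 4.9 and Tables 14.3.6 to 14.3.9:

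- Keep the by-visit rows as they are.
- State that readings on the Unscheduled Visit page are not assigned to a nominal visit but do enter the new rows below.
- For each eye, add the number and percentage of subjects with the event at any post-insertion assessment, scheduled or unscheduled: IOP ≥30 mmHg, IOP rise >5 and >10 mmHg, and BCVA loss ≥3 lines. Add the worst post-insertion slit-lamp and fundus category.
- Show the number of unscheduled assessments per arm beside these rows.

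The cost is a short SAP revision and one block of rows per table. The visit schedule and data collection do not change. The drawback is uneven ascertainment: subjects with more visits have more chances to be counted. The assessment counts let a reader judge this, and the by-visit rows remain the comparison made on equal schedules.
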